11.1 Applicable SOPs

AEs definition, classification and management will follow the Sponsor SOPs, based upon applicable local and international regulations. CRO shall submit SUSARs according to local law.

A brief summary of AE definition, classification and management is reported below.

11.2 Definitions

11.2.1 Adverse Events

An adverse event (AE) is defined as any untoward medical occurrence in a patient or clinical investigation subject administered a medicinal product and which does not necessarily have a causal relationship with this treatment. An AE can therefore be any unfavorable and unintended sign (including an abnormal laboratory finding), symptom, or disease temporally associated with the use of a medicinal product, whether or not related to the medicinal product.

11.2.2 Adverse Drug Reaction

An Adverse Drug Reaction (ADR) is defined as an adverse experience which is a reasonably likely to have been caused by the drug. Adverse events are to be considered unsuspected if the relationship to the study drug as described in the table in section 11.5.2 is none or unlikely; whereas any AE reported in the study having a possible, probable or highly probable relationship to study drug will be considered as an ADR. The definition covers also medication errors and uses outside what is foreseen in the protocol, including misuse and abuse of the product.

11.2.3 Serious Adverse Event (SAE) Definition

A serious adverse event (SAE) is defined as any untoward medical occurrence that at any dose:

- results in death
- is life-threatening (i.e. the subject was at risk of death at the time of the event. It does not refer to an event which hypothetically might have caused death if it were more severe),
- requires inpatient hospitalization or prolongation of existing hospitalization

(NOTE: In general, hospitalization means that the individual remained at the hospital or emergency ward for observation and/or treatment (usually involving an overnight stay) that would not have been appropriate in the physician's office or an out-subject setting. Complications that occur during hospitalization are AEs. If a complication prolongs hospitalization or fulfills any other serious criteria, the event is serious.

When in doubt as to whether “hospitalization” occurred, the event should be considered serious)

- results in persistent or significant disability/incapacity

(NOTE: This definition is not intended to include experiences of relatively minor medical significance such as uncomplicated headache, nausea, vomiting, diarrhea, influenza, or accidental trauma (e.g., sprained ankle) which may interfere or prevent everyday life functions, but do not constitute a substantial disruption)

- is a congenital anomaly/birth defect
- is medically significant or important medical condition, i.e. an important medical event that based upon appropriate medical judgment, may jeopardize the subject and may require medical or surgical intervention to prevent one of the outcomes listed above

(NOTE: An important medical condition is an event that may not result in death, be life-threatening, or require hospitalization but may be considered a SAE when, based upon appropriate medical judgment, it may jeopardize the subject’s wellbeing and may require medical or surgical intervention to prevent one of the outcomes listed above. Examples of such medical events include allergic bronchospasm requiring intensive treatment in an emergency room or at home, blood dyscrasias or convulsions that do not result in subject hospitalization, or the development of drug dependency or drug abuse)

11.3 Unexpected Adverse Reaction

An ADR is considered unexpected if it is not listed in the Investigator Brochure (Reference Safety Information section). An event is unexpected also when it is not listed at the specificity or severity that has been observed and listed in the Investigator Brochure. Events that are mentioned in the Investigator Brochure as occurring with a class of drugs or as anticipated from the pharmacological properties of the drug, but are not specifically mentioned as occurring with the particular drug under investigation are considered unexpected.

The determination of expectedness shall be made on the basis of the IB Reference Safety Information (RSI) section.

11.3.1 Reference Safety Information (RSI)

As reported in the Reference Safety Information section of the Investigator’s Brochure, considering the development phase of the compound and the low number of total subjects exposed to ladarixin, adverse events/reactions (notwithstanding seriousness) should be considered unexpected at this stage.

11.3.2 Suspected Unexpected Serious Adverse Reaction (SUSAR)

A SUSAR is defined as an ADR that is both unexpected (not consistent with the RSI) and also meets the definition of a SAE.

11.4 Monitoring for Adverse Events

At each visit following study informed consent form signature, after the subject has had the opportunity to spontaneously mention any problems, the Investigator or appropriate designee should inquire about AEs by asking the standard questions:

- “Have you had any health problems since your last study visit?”
- “Have there been any changes in the medicines you take since your last study visit?”

AEs should be reported for any clinically relevant change in concomitant condition(s) that is the result of an untoward (unfavorable and unintended) change in a subject's medical health. Changes in any protocol-specific systemic parameter evaluated during the study are to be reviewed by the Investigator. Any untoward (unfavorable and unintended) change in a protocol-specific parameter that is clinically relevant is to be reported as an AE. These clinically relevant changes will be reported regardless of causality.

11.5 AEs recording

AEs will be collected and recorded for any untoward event that occurs in a subject from the time he or she signs the ICF for the trial until last follow-up visit/ETV. Thus, any untoward medical occurrences or unfavorable and unintended signs, symptoms, or diseases that occur in the pre-treatment [pre-treatment AE (PTAE)], in treatment or post-treatment [treatment-emergent AE (TEAE)] period are to be considered AEs and/or SAEs, and consequently recorded and reported as such. Should a non-serious AE become serious, the Investigator will then follow the same reporting procedures as for SAEs.

An AE occurring after the last follow-up visit/ETV and coming to knowledge of the investigator (e.g. by spontaneous reporting by study subjects) must be recorded only if it is an ADR, according to the investigator's judgment

Each AE will be described by:

- Its duration (start and stop dates).
- Severity grade.
- Its relationship to the study drug; (suspected/unsuspected).
- Action(s) taken.
- Outcome.

11.5.1 Severity of AEs

The Investigator will grade the severity of any AE using the definitions in the table below. For each episode, the highest severity grade attained should be reported.

Mild	Grade 1 - Does not interfere with subject's usual function (awareness of symptoms or signs, but easily tolerated [acceptable]).
Moderate	Grade 2 - Interferes to some extent with subject's usual function (enough discomfort to interfere with usual activity [disturbing]).
Severe	Grade 3 - Interferes significantly with subject's usual function (incapacity to work or to do usual activities [unacceptable])

11.5.2 Relationship of AEs to the IMP

The Investigator will assess the causal relationship between the AE and the IMP, according to the criteria in table below:

None (Intercurrent Event)	An event that is not and cannot be related to the Investigational Product, e.g. subject is a passenger in a road traffic accident.
Unlikely (remote)	Relationship is not likely e.g. a clinical event including laboratory test abnormality with temporal relationship to drug administration which makes a causal relationship improbable and in which other drugs, chemicals or underlying disease provide more plausible explanations
Possible	Relationship may exist, but could have been produced by the subject's condition or treatment or other cause
Probable	Relationship is likely, the AE abates upon discontinuation of Investigational Product and cannot be due to the subject's condition
Highly Probable	Strong relationship, the event abates upon discontinuation of Investigational Product and, if applicable, re-appears upon repeat exposure

11.6 SAEs reporting

The Investigator must report all SAEs, regardless of presumed causal relationship, to Dompé Pharmacovigilance and to the CRO, by email (preferred) or fax within 24 hours of learning of the event. Contact details for SAE reporting are the following

Sponsor

Dompé Pharmacovigilance
 Email: [contact]
 [contact]

CRO:

Email: [contact]
 [contact]

The investigator should also report information on SAEs that continue after subject has completed his/her participation in the study (whether study completion or withdrawal), unless subject has withdrawn his/her consent.

Information on SAEs will be recorded on the SAE form. Follow-up reports (as many as required) should be completed and faxed/e-mailed following the same procedure above, marking the SAE form as "follow up Number XX".

Whenever more than one SAE is observed, the Investigator should identify which is the primary adverse event, i.e. the most relevant one. If other events are listed in the same report, the Investigator, along with their relatedness to the IMP, should identify which adverse events are serious and which are non-serious. In any case, the Investigator is requested to record his/her opinion about the relatedness of the observed event(s) with the investigational medication.

In line with CT3 Detailed Guidance and ICH E2A provisions, although the Investigator does not usually need to actively monitor subjects for AEs once the trial has ended, if the Investigator becomes aware of a SAE occurring to a subject after that subject has ended his/her participation in the study (whether study completion or withdrawal), the SAE should be reported by the Investigator to the Dompé Pharmacovigilance. Such “post-study cases” should be regarded for expedited reporting purposes as though they were study reports. Therefore, a causality assessment and determination of expectedness are needed for a decision on whether or not expedited reporting is required.

11.6.1 Adverse events exemption

Not applicable; no adverse event reporting exemption.

11.7 Reporting Procedure to IRB/IEC and to Regulatory Authorities

During the course of the clinical trial, Dompé farmaceutici S.p.A shall report any serious unexpected ADR (SUSAR) to the Competent Authority (according to specific law requirements) while the CRO shall submit SUSARs (as per final report released by Dompé) to the concerned IEC which approved the protocol as soon as possible and in no event later than:

- (a) seven (7) calendar days after becoming aware of the information if the event is fatal or life threatening;
- (b) fifteen (15) calendar days after becoming aware of the information if the event is neither fatal nor life threatening.

Dompé farmaceutici S.p.A. shall, within eight days after having informed the IEC/Competent Authority under paragraph (a), submit a complete report in respect of that information that includes an assessment of the importance and implication of any findings, made on the basis of follow up information provided by the Investigator.

The Sponsor shall be responsible to prepare and submit periodical update reports as appropriate.

Copies of all correspondence relating to reporting of any SAEs to the IEC/IRB should be maintained in the Investigator's Files.

11.8 Follow-up of Subjects with Adverse events

AE will be followed by the Investigator (by phone or visit) until resolved or considered stable.

The Investigator is responsible for adequate and safe medical care of subjects during the trial and for ensuring that appropriate medical care and relevant follow-up procedures are maintained after the trial. It is the Investigator's responsibility to assure that the subjects experiencing AEs receive definite treatment for any AE, if required.

For pharmacovigilance purposes, all SAEs should be followed-up in order to clarify as completely as possible their nature and/or causality and until all queries have been resolved. All SAEs will be followed up until the events resolve or the events or sequelae stabilize, or it is unlikely that any additional information can be obtained after demonstration of due

diligence with follow-up efforts (i.e. subject or Investigator is unable to provide additional information, or the subject is lost to follow up), unless subject has withdrawn his/her consent.

If subject was hospitalized due to a SAE, a copy of the discharge summary is to be forwarded to the Sponsor as soon as it becomes available. In addition, a letter from the Investigator that summarizes the events referred to the case, as well as results of any relevant laboratory tests and redacted section of medical records may be provided to the Sponsor, if relevant for the SAE. In case of death, a copy of the autopsy report, if performed, should also be provided.

The Investigator shall inform the Sponsor with an appropriate written communication, whenever he becomes aware of new available information regarding the SAE, once the condition is resolved or stabilized and when no more information about the event is expected. Follow-up SAE information should be processed as initial SAE notification.

11.9 Pregnancy in the Clinical Trial

Women of childbearing potential are not excluded from the study as long as adequate birth control methods are being utilized. Women of childbearing potential are defined as all women physiologically capable of becoming pregnant. Adequate birth control methods are summarized in the protocol's exclusion criteria.

Prior to enrolment in the clinical trial, female subjects of childbearing potential and their partners must be advised of the importance of avoiding pregnancy during the entire course of the study treatment and for the 30 days after the study treatment period ends and of the potential risks associated with an unintentional pregnancy. During the trial, female subjects are to be instructed to contact the Investigator immediately if they suspect they might be pregnant.

Pregnant female subject will discontinued the study. Pregnancy is not reportable as an adverse event; however, complications may be reportable and will be assessed for reportability on a case by case basis. A form prepared by the Sponsor will be utilized to capture all pregnancy-related information until the birth of the child during the study treatment period and follow-up period.

11.10 OVERDOSE

Accidental or intentional overdose, which may or may not result in serious adverse reactions, is to be reported to Dompé Drug Safety/CRO and Dompé Medical Expert, following the same procedure for SAE, within 24 hours from the Investigator's knowledge of its occurrence. This includes reports related to drug intake through different routes (e.g. ingestion) or with suicidal intentions and consequent drug overdose.

An overdose of ladarixin is defined as the administration of 6 or more capsules on any given treatment day.

The Investigator shall provide in the SAE form information about symptoms, corrective treatment and outcome of overdose. Dompé Medical Expert should be contacted to discuss corrective treatment, if necessary.

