3 CLINICAL SUPPLIES

3.1 Treatment

3.1.1 *Description of product*

The analytical certificate will be supplied with the investigational medicinal product (IMP).

3.1.1.1 *Test product*

IMP	Ladarixin 200 mg hard gelatin capsules
Distributor	Dompé farmaceutici S.p.A., Italy
Manufacturer (active substance)	AMSA S.p.A, Como, Italy
Manufacturer (finished product)	Depo Pack s.n.c., Saronno (Va), Italy
Pharmaceutical form	Hard gelatin capsules
Dose	400 mg (two 200 mg capsules)
Administration route	Oral

3.1.2 *Dose regimen*

A single oral dose of 400 mg of ladarixin (two 200-mg capsules) will be administered to healthy male and female volunteers under fed (T treatment) and fasting (R treatment) conditions in 2 study periods, according to a two-way crossover design, with a wash-out interval of at least 14 days between the two administrations.

3.1.3 *Route and method of administration*

The IMP will be orally administered on day 1 of each period, at $8:00 \pm 1$ h. In detail, at each dosing, 2 capsules will be swallowed with 240 mL of still mineral water, without chewing.

The subjects allocated to the fed conditions will receive the IMP 30 min after having started to eat a high-fat and high-caloric breakfast (§ 6.2.1), while the subjects allocated to the fasting conditions will receive the IMP under prolonged fasting conditions (at least 10 h pre-dose).

The investigator will check that all subjects take the IMP appropriately.

3.1.4 *Investigational product distribution*

The IMP will be administered by the investigator or by his/her deputy at the Phase I Unit. The IMP will be exclusively used for the present clinical study and will only be administered to the subjects enrolled in the study.

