3.2 Packaging and labeling

The Phase I Unit will be provided with 36 subject's individual boxes (subject kits). Each subject's kit will contain 2 boxes (one for each study period), each containing 2 blisters of 1 200-mg capsule of ladarixin.

The sponsor will provide a reserve kit for each subject to be used if needed. Subject kits will be numbered from 001 up to 036. Reserve subject kits will be numbered as 001R-036R.

The formulation labeling will report all the information requested according to the Annex 13 to the Good Manufacturing Practice (published by the Commission in The rules governing medicinal products in the European Community, Volume 4; 10) as follows:

- a. Name, address and telephone number of the Sponsor, contract research organization or investigator (the main contact for information on the product and clinical study)
- b. Pharmaceutical dosage form, route of administration, quantity of dosage units, the name/identifier and strength/potency
- c. The batch and/or code number to identify the contents and packaging operation
- d. A study reference code allowing identification of the study, site, investigator and Sponsor if not given elsewhere
- e. The study subject identification number and where relevant, the period number
- f. The name of the investigator (if not included in (a) or (d))
- g. Directions for use (reference may be made to a leaflet or other explanatory document intended for the study subject or person administering the product)
- h. "For clinical study use only" or similar wording
- i. The storage conditions
- j. Period of use (use-by date, expiry date or re-test date as applicable), in month/year format and in a manner that avoids any ambiguity
- k. "Keep out of reach of children"

Labels will be in English language.

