3.4 Drug accountability

The IMP will be provided as individual subject's kits directly to the investigator by the sponsor, in excess of the amount necessary for the study (100% excess).

After receipt of the IMP supply, the pharmacist will confirm in writing by signing and dating standard drug accountability forms.

At the end of the study, used, unused and partially used supplies of the IMP provided by the Sponsor will either be destroyed on site (upon written authorization) or returned to the Sponsor after assessment of drug accountability.

In the event that the IMP will be destroyed on site, a destruction certificate will be provided to the sponsor.

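### Minor: the 24-hour overdose report in Protocol section 11.10 starts at 6 capsules in a 2-capsule trial, so the protocol text gives a non-serious intake of 3 to 5 capsules no prompt notification

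*Protocol*

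**What the plan says.** Dose (Protocol 3.1.2): "A single oral dose of 400 mg of ladarixin (two 200-mg capsules) will be administered", once fed and once fasting, in two periods. The investigator or a deputy gives the capsules at the unit (3.1.4), and under 3.1.3 "The investigator will check that all subjects take the IMP appropriately".

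Supplies (3.2): each subject's kit has one box per period, "each containing 2 blisters of 1 200-mg capsule of ladarixin". In addition, "The sponsor will provide a reserve kit for each subject to be used if needed". Section 3.4 describes the supply as a 100% excess.

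Overdose (11.10): the rule covers "Accidental or intentional overdose, which may or may not result in serious adverse reactions". Such an event is reported by the SAE procedure within 24 hours of the investigator learning of it, and the sponsor's medical expert is to be contacted about corrective treatment if needed. The definition follows: "An overdose of ladarixin is defined as the administration of 6 or more capsules on any given treatment day".

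Section 11 presents itself as a brief summary. Section 11.1 says "AEs definition, classification and management will follow the Sponsor SOPs", and 13.3 repeats this for AEs and SAEs.

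**The concern.** Section 11.10 is meant to catch overdoses that cause no serious harm as well as those that do. Its trigger, however, lies above anything that can happen with one subject's own supply. If a subject received both period boxes on one day, the dose would be doubled, yet it would not count as an overdose. Neither the 24-hour notice nor the instruction to involve the medical expert would then apply. The protocol gives no reason for choosing six.

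What is at stake is the timing and routing of a safety notification after a dosing error without a serious event. Section 1.6 reports good tolerability so far but adds that the small numbers rule out overall conclusions on safety, so early sight of such an error by the sponsor has some value. No endpoint or estimate is involved.

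**Working it through.** **Inputs.** Capsule strength 200 mg and planned dose 2 capsules = 400 mg (3.1.2). Trigger 6 capsules (11.10). Kit of 2 boxes with 2 capsules each (3.2). Reserve kit taken to be the same size as the subject kit, in line with the 100% excess in 3.4. 36 subjects and 2 periods (10.2, 3.1.2).

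**Step 1: the trigger in mg.** 6 × 200 = 1200 mg; 1200 / 400 = 3.0 times the planned dose.

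**Step 2: intakes around the trigger.** Amount = capsules × 200 mg; multiple = amount / 400 mg.

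| Capsules | Amount | Multiple of planned dose | Overdose under 11.10? |
|---|---|---|---|
| 2 | 400 mg | 1.0 | no (planned dose) |
| 3 | 600 mg | 1.5 | no |
| 4 | 800 mg | 2.0 | no |
| 5 | 1000 mg | 2.5 | no |
| 6 | 1200 mg | 3.0 | yes |

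**Step 3: what one subject's supply allows.** Own kit: 2 × 2 = 4 capsules = 800 mg. Shortfall to the trigger: 6 − 4 = 2 capsules, i.e. one further box. Own kit plus reserve kit: 8 capsules = 1600 mg. The rule is therefore reached only if capsules from a reserve kit or from another subject's kit are used as well.

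**Step 4: is there another prompt route for a non-serious intake of 3 to 5 capsules?**

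- 11.6 sets a 24-hour limit, but for SAEs only.
- 11.2.2 brings medication errors under the ADR definition, without a reporting time.
- 10.1.2 has administration errors that could make the PK profile unreliable noted in the eCRF, without notification.
- 11.5 has AEs recorded, again without a 24-hour limit.

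None of these sets a clock.

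**Step 5: opportunity.** 36 × 2 = 72 planned administrations, all supervised, so few such errors, if any, are to be expected.

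**The case against.** **Prior exposure.** A reader might infer that the trigger is three times the highest dose given before, so that a doubled dose would be new territory. The documents do not support that. The threshold is set per treatment day, so daily amount is the natural comparator, and section 1.4.3 describes 12-hourly dosing on days 3 to 7 in the 300 and 400 mg cohorts. If 400 mg was each dose, 800 mg/day has already been given. The trigger is then 1200 / 800 = 1.5 times that, and 3, 4 and 5 capsules are 0.75, 1.0 and 1.25 times. Assuming linear one-compartment kinetics and the half-life of about 13.6 h in the protocol's tables, accumulation at 12-hour dosing is 1 / (1 − exp(−0.693 × 12 / 13.6)), about 2.2. A single 800 mg intake, at about twice the single-dose peak and AUC, would then stay within exposure already studied. Section 1.4.1 instead says once daily, in which case 400 mg/day is the comparator and all three intakes exceed it. Phase II doses are not stated. This objection stands against any ratio to earlier studies, and the point here does not use one.

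**A legitimate threshold.** A clinical overdose limit above the planned dose can be a sound tolerability judgement, and its basis may be in the Investigator's Brochure. That also stands: the documents do not show that six is clinically wrong. It does not explain why the notification duty has to share that limit.

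**SOPs.** Sponsor procedures that are not shown govern AE management and may already require prompt notice of medication errors. Whether there is a gap in practice therefore cannot be settled. The claim is confined to the protocol text.

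**Remoteness and cover.** Subjects do not hold their kits, each period has its own box, and staff give the dose and check it. A reader might infer that a 3 to 5 capsule error would go unrecorded or unobserved. It would not: subjects stay confined until the morning of day 4 (6.2.2), AEs are recorded, errors that could affect the profile are noted, and serious or medically important events go to the sponsor within 24 hours (11.2.3, 11.6). This limits the size of the point without supplying the missing notification.

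**Conclusion.** The point holds as a minor one. Measured against this trial's own dose, the overdose rule is badly fitted: its trigger is 3.0 times the dose and exceeds a subject's entire 4-capsule supply, although the rule is meant to cover non-serious accidental overdose too. Within the protocol text, 600, 800 and 1000 mg taken without a serious event have no 24-hour route to the sponsor's drug safety unit and medical expert.

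The consequence is limited to when and how the sponsor is told. The conclusion assumes that the protocol text is read without the sponsor's SOPs; if those already set a prompt route, the protocol is incomplete on this point but practice is not. The planned PK analysis is unaffected.

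**What to change.** Add one sentence to section 11.10: any administration of more than 2 capsules (400 mg) on a dosing day is reported by the same 24-hour route, with or without an adverse event. Six capsules may stay as the clinical overdose threshold, preferably with its reason stated.

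The cost is one sentence and at most a few extra expedited reports, unlikely under supervised dosing. The note to file of 19 January 2021 says the clinical phase had ended and the protocol would not be amended, so the change is of practical use mainly where this wording is carried into later ladarixin protocols.
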